1. INTRODUCTION

Exercise-based cardiac rehabilitation (CR) has been shown to consistently reduce the rates of total and cardiovascular-related mortality and morbidity [1, 2]. Cardiac rehabilitation is often prescribed for those who have experienced a cardiac event and follows Canadian guidelines to achieve a minimum of 30 minutes of moderate-to-vigorous intensity physical activity (MVPA) on at least five days per week [3]. Although current CR guidelines focus on MVPA, sedentary behaviours have gained recent attention as strong and modifiable risk factors for heart disease. Specifically, they have an effect on cardio-metabolic functioning and are strongly associated with several markers of cardio-metabolic risk [4]. Recent data from the University of Ottawa Heart Institute (UOHI) shows that CR graduates spend the majority of their wakeful time sedentary and this time is negatively associated with body mass index (BMI) and measured cardiorespiratory fitness [5].

UOHI offers a supervised on-site 8-week CR program. The program consists of twice-weekly sessions (1 hour each) with a focus on aerobic and resistance exercise. There is currently no intervention component or outcome measure focusing on sedentary behaviours. This is unfavorable given the knowledge of the impact of sedentary behaviours on cardio-metabolic health. It is important to assess sedentary behaviours in this population to assess whether current programming affects sedentary behaviours or if more is needed to target these behaviours. This is important to note given that physical activity (PA)-focused interventions do not generally result in clinically meaningful reductions in sedentary behaviours [6]. Therefore, it is important to also investigate the feasibility of adding sedentary behaviour interventions to CR programming and whether these interventions can consequently further improve cardio-metabolic health. Using cues and prompting from wearable technology may provide a feasible way to reduce sedentary behaviours. A recent systematic review noted that interventions using education and prompts/cues were promising for reducing sedentary behaviours [7]. To date, most research using direct measures of PA and sedentary time have used research-grade accelerometers (e.g. ActiGraph®, Actical®, etc.). Research has shown that these monitors are not as valid for measuring sedentary time and postural changes as the *activPAL3™* monitor which is more precise and sensitive to changes in sedentary time [8].

The *activPAL3™* monitors have the capability to discern between standing and sitting which can increase our knowledge of movement patterns among CR participants. Additionally, the development of the *activPAL3™ VT* (VTAP) with vibrotactile feedback (VT), offers direct feedback to the wearer regarding time spent being sedentary. The prompts provided by these monitors have the capacity to reduce sedentary time and increase breaks from prolonged sitting by promoting individual awareness around movement patterns.

2.0 PURPOSE

This research is timely given recent interest in the role of sedentary behaviours in both the primary and secondary prevention of cardiovascular disease. Sedentary behaviours have been shown to be high in patients with cardiovascular disease [5] and it is not yet known if current CR programming results in significant reductions of these behaviours, or whether a targeted component is warranted. It is also unclear if self-reported sedentary time measures can provide valid and reliable information for monitoring these behaviours in a CR setting, or whether more objective measures such as the *activPAL3™* are needed. This study has multiple purposes:

1. To inform the development of a larger randomize controlled trial;
2. to assess the feasibility and usability of the *activPAL3™* devices for measuring sedentary time in a CR setting and identify how it compares to self-report methods.
3. to describe changes in sedentary time that occur over standard CR with the use of prompting cues from the VTAP; and
4. to assess whether the addition of prompting cues can result in further decreases in sedentary behaviour and improvements in clinical outcomes, health-related quality of life (HRQoL), symptoms of anxiety and depression, self-efficacy, aortic stiffness, and aerobic capacity.

Results from this study will inform current gaps in the literature and help to generate recommendations for whether targeting sedentary behaviours in the CR setting is warranted.

3.0 KEY TERMS AND DEFINITIONS

3.1 Sedentary time

Sedentary time refers to the amount of time spent engaged in sedentary behaviours. Sedentary behaviour refers to an energy expenditure of 1.5 metabolic equivalents (METS; measure of energy expenditure) or less while in a sitting or reclining posture during waking hours and not simply the absence of PA [4]. This study will collect both self-reported and objectively measured sedentary time.

3.2 Physical activity (PA)

PA refers to “any bodily movement produced by the skeletal muscle that results in energy expenditure” [9]. This study will employ the use of both self-reported and objectively measured PA, specifically of moderate-to-vigorous intensity (MVPA).

4.0 OBJECTIVES

4.1 Primary objective

The primary objective of this study is to evaluate the feasibility and usability of the VTAP to reduce sedentary time and the *activPAL3™* monitors to quantify changes in free-living time spent sitting, standing and lying in CR patients in the UOHI on-site cardiac rehabilitation program (SIT-CR Study).

4.2 Secondary objectives

Secondary objectives include:

1. quantifying sedentary time (including time spent sitting, standing and lying) in CR patients (control arm);
2. assessing the possible effect of an on-site CR program on reducing time spent being sedentary (control arm);
3. evaluating whether the addition of sedentary prompts (Intervention group [I]) leads to further reductions in sedentary time, beyond those achieved through regular CR (Control group [C]);

4. validating a CR-specific PA and sedentary time log; and
5. evaluating the impact of the Intervention on: clinical outcomes (e.g., blood pressure, resting heart rate, blood lipids, blood sugar, body weight, body mass index [BMI], waist circumference, aortic stiffness); health-related quality of life [HRQoL]; self-efficacy; symptoms of anxiety and depression); MVPA; and maximal aerobic power (VO₂max).

4.3 Hypotheses

In adults with a diagnosis of coronary artery disease (CAD) (including heart attack, angina (chest pain), stent, percutaneous coronary intervention (PCI), and/or bypass surgery (CABG), providing sedentary prompts using a thigh-worn activity monitor (VTAP) will be superior to standard 8-week on-site CR programming in:

1. decreasing sedentary time;
2. increasing breaks from sedentary time;
3. increasing MVPA;
4. improving clinical outcomes (e.g. blood pressure, resting heart rate, blood lipids, HbA1c, body weight, BMI, waist circumference)
5. improving HRQoL, self-efficacy, symptoms of anxiety and depression;
6. improving measures of aortic stiffness; and
7. increasing maximal aerobic power (VO₂max).

5.0 METHODS

5.1 Study design

This is a single-centre, two-armed randomized controlled trial (RCT) to evaluate the feasibility and usability of the *activPAL3™* in measuring sedentary time and the VTAP in providing sedentary prompts to reduce sedentary time in a CR setting (SIT-CR Study). The RCT (see **Figure 1** for study flow) will randomly allocate 32 individuals (16 males and 16 females) in a 1:1 ratio entering the CR program to either the Control Group (CR program) or to the Intervention Group (CR program + sedentary prompts from VTAP).

A week prior to their first class, participants will be asked to come to the UOHI to complete informed consent, a short questionnaire to assess employment patterns, self-efficacy to reduce sedentary behaviour and increase light and moderate PA, and HRQoL (see SIT-CR Study Baseline and Follow-up Questionnaires). Participants will also have their aortic stiffness, blood pressure and resting heart rate measured. In order to test for aortic stiffness participants will be asked to fast if possible, the study will provide a package of nuts and a glass of water at this first meeting. After the measurements, participants will then be asked to wear an *activPAL3™* during waking time for 7 days to collect baseline measures of sedentary time over one week prior to their first CR class.

On the day of their first CR class, participants will be asked to come in 30 minutes early to complete a Modified Bruce Ramp Treadmill Test to estimate maximal aerobic power. Once the test is complete, participants will be randomized in a 1:1 ratio (stratified by sex) to the Intervention or Control Groups. At this visit, participants in the Intervention Group will receive a wear time log sheet and a VTAP

monitor that will provide sedentary prompts to break up prolonged periods of sedentary time (prompts after 30 minutes of sedentary time). Participants in the Intervention Group receive a full-charged VTAP monitor each week when they attend their on-site CR class. Participants in the Control Group will continue with their regular CR class schedule.

Follow-up sedentary time measures will be taken at the end of CR (during Week 8 of CR/Week 9 of the RCT), participants will be asked to once again wear an *activPAL3™* during waking time for 7 days. Participants will be asked once again to complete a short questionnaire to assess employment patterns, self-efficacy to reduce sedentary behaviour and increase light and moderate PA, and HRQoL (see SIT-CR Study Follow-up Questionnaires). They will also have their arterial stiffness, blood pressure and resting heart rate measured and will once again be asked to complete a Modified Bruce Ramp Treadmill Test during this last week.

As part of the regular CR program standard of care, clinical measures will be taken (e.g. blood lipids, HbA1c, body weight, BMI, waist circumference) and depression and anxiety will be self-reported (see CR Questionnaire) at both baseline and follow-up.

The 8 week intervention time period was chosen to align with current CR programming to allow for comparisons between the intervention and standard CR programming (control group). As sedentary behaviour intervention research is currently in its infancy, it is unknown how long an intervention is required; therefore, this investigation will provide pilot-level information to inform whether 7 weeks of intervention is adequate and whether it is feasible to add to the pre-existing CR programming. Previous studies have shown significant reductions in sedentary time following 4 to 24 weeks of intervention [10-14].

[figure not shown]

Figure 1. Study schema

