5.5 Measures

The primary objective of this study is to assess the feasibility and usability of the *activPAL3™* and the VTAP in a CR setting to inform the development of a larger RCT. This will be assessed by examining:

- Recruitment rates;
- acceptability of intervention and wearing the *activPAL3™* and the VTAP using an evaluation survey (see Evaluation Surveys);
- completion and drop-out rates; and
- intervention adherence using wear time logs.

The primary outcome of the intervention focuses on changes in sedentary time measured by self-report and the *activPAL3™* over the 8-week intervention period. These outcomes will provide standard deviations to estimate an effect size for a future RCT. Secondary outcome measures will include:

- changes in MVPA (self-reported and objectively measured);
- changes in clinical outcomes (e.g., body weight, BMI, waist circumference, blood pressure, total cholesterol, HDL, LDL, triglycerides, and fasting plasma glucose);
- changes in measures of anxiety and depression (HADS);
- changes in self-efficacy to reduce sedentary time and increase PA;

- changes in HRQoL (SF-36);
- changes in aortic stiffness (PWV); and
- changes in maximal aerobic power (Modified Bruce Ramp Treadmill Test).

Measures and study time-line are provided in **Table 1**.

5.5.1 *Sedentary time*

The primary objective of this study is to evaluate the feasibility and usability of the *activPAL3™* in collecting time spent sitting, standing and lying in an on-site CR program. From this, the primary outcome of the RCT will be changes in sedentary time as measured both by self-report (sitting time from the International Physical Activity Questionnaire [see SIT-CR Baseline and Follow-up Questionnaires], sitting time from a FITS log [see SIT-CR Baseline and Follow-up Questionnaires], a sitting time question from the CR intake questionnaire), and objectively measured by the *activPAL3™* over 7-days. See the provided PAL Technologies Ltd. End User Licence Agreement.

5.5.2 *Moderate-to-vigorous intensity physical activity (MVPA)*

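### On the written sequence, the baseline IPAQ sitting item is answered before the activPAL3 week begins, so that one comparison mixes reporting error with week-to-week change

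*Combined protocol and SAP*

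**What the plan says.** Section 2.0 gives as one purpose assessing the activPAL3 in cardiac rehabilitation (CR) and to "identify how it compares to self-report methods". Section 4.2 adds the objective of "validating a CR-specific PA and sedentary time log".

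Section 5.5.1 names three self-report sources for sitting time. Two are cross-referenced to the study's own questionnaires: "sitting time from the International Physical Activity Questionnaire [see SIT-CR Baseline and Follow-up Questionnaires], sitting time from a FITS log". The third is "a sitting time question from the CR intake questionnaire".

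On baseline timing, section 5.1 states: "A week prior to their first class, participants will be asked to come to the UOHI to complete informed consent, a short questionnaire". After that visit's measurements, participants wear the activPAL3 for 7 days "to collect baseline measures of sedentary time over one week prior to their first CR class". Section 5.4.1 gives the same order, with the questionnaire first and the monitor afterwards. It also has the FITS log filled in daily during the wear week, for data verification and for validating self-reported sedentary time.

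On follow-up, section 5.1 puts both the wear and the questionnaire in CR week 8: "Participants will be asked once again to complete a short questionnaire to assess employment patterns". It does not say which comes first. Table 1 lists activPAL3, IPAQ and the CR questionnaire in one row, marked for the baseline week and for week 8/follow-up, without day or order.

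**The concern.** A questionnaire completed before the monitor is fitted cannot report on the days the monitor then records. If the IPAQ item is answered at the baseline visit, three things are combined in its disagreement with the activPAL3: error in the self-report, ordinary change from one week to the next, and any change in behaviour caused by starting to wear a monitor. Only the first bears on whether the item is usable in CR. The pilot could judge the IPAQ item less accurate than it is.

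Follow-up raises a further possibility. Prompts run in weeks 1 to 7 only. If the IPAQ is completed when the monitor is issued in week 8, an intervention participant could be recalling the last prompted week while the activPAL3 records an unprompted one. Controls have no such switch. Self-reported and device-measured sitting are both part of the declared primary outcome, so the two could then differ between arms partly because of timing.

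**Working it through.** The plan states no figure for this point, so there is none to reproduce. The check has two parts.

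**1. Which days each baseline measure covers**

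| Measure | When completed | Same days as the activPAL3? |
|---|---|---|
| activPAL3 | 7 days after the baseline visit (5.1, 5.4.1) | reference |
| FITS log | daily over the same 7 days (5.4.1) | yes |
| IPAQ sitting item | in the SIT-CR questionnaire (5.5.1), which is completed at the visit before wear (5.1, 5.4.1) | no, on the written sequence |
| CR sitting item | in the CR intake questionnaire (5.5.1) | not tied to the monitored days |

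No section gives an IPAQ recall period or defers the item until after wear.

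**2. How much the mismatch could matter (illustration only)**

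Inputs:
- SD of sedentary time: 94 min/day (section 5.6.1).
- Week-to-week intraclass correlation (ICC): not in the documents; 0.7, 0.8 and 0.9 are assumed.
- A self-report that is perfect for the week it describes, and the same SD in both weeks.

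Formulas:
- SD of the between-week difference = 94 × √(2 × (1 − ICC)).
- 95% limits of agreement around the mean difference = ±1.96 × that SD.
- Standard error of the mean difference with all 32 participants = that SD / √32.

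| ICC | SD of difference (min/day) | Limits of agreement (min/day) | SE of mean (min/day) |
|---|---|---|---|
| 0.7 | 94 × √0.6 = 72.8 | ±143 | 12.9 |
| 0.8 | 94 × √0.4 = 59.5 | ±117 | 10.5 |
| 0.9 | 94 × √0.2 = 42.0 | ±82 | 7.4 |

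Under this model the correlation between a perfect report of one week and the device value of the next equals the ICC, so it could not exceed 0.7 to 0.9. The limits of agreement and the correlation suffer most. The mean difference is affected less: timing adds a standard error of about 7 to 13 min/day, and no bias if average sitting is the same in both weeks.

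**The case against.** **The FITS log already supplies a same-week comparison.** This stands. A reader might infer that the trial cannot show how device and self-report agree. The documents do not support that: the log is concurrent with wear, is intended for validation, and a log is the only instrument with a validation objective of its own. But agreement of a daily diary does not establish agreement of a single recall item, so the IPAQ question remains.

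**The IPAQ's completion day is inferred.** This also stands. Sections 5.1 and 5.4.1 list what the questionnaire assesses and do not name the IPAQ. The FITS log carries the same cross-reference and is not filled in at the visit. Table 1 lists the IPAQ apart from the other questionnaires. If later completion is intended, the protocol needs only to say so.

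**The recall period is unknown.** If the item asks about usual sitting, the two-week model overstates the effect. A perfect report of a person's long-run mean would differ from one week's device value with SD 94 × √(1 − ICC), which is 51, 42 or 30 min/day for the three ICCs. The answer would still not be tied to the monitored days.

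**The between-arm effect at follow-up is conditional.** A reader might infer that the IPAQ and activPAL3 will recall different prompting conditions in the intervention arm. Section 5.1 does not give the order within week 8, so this is only a possibility that the protocol should close off.

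**Not every item can be moved freely.** The CR intake sitting item belongs to standard care, and section 6.2 says usual care will not change. No visit for returning the monitor after the follow-up wear is described.

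**Conclusion.** The concern holds for the baseline IPAQ-versus-activPAL3 comparison, as the protocol is written. That comparison covers different days and has no stated recall period, so its spread of disagreement cannot be read as reporting error alone. The conclusion rests on the IPAQ being completed with the rest of the questionnaire it sits in. The size rests on the plan's SD of 94 min/day and on assumed ICCs: limits of agreement of about ±143 to ±82 min/day from timing alone for ICCs of 0.7 to 0.9, and narrower if the item asks about usual sitting.

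The FITS comparison is unaffected. Mean IPAQ bias remains estimable if average sitting is stable across the two weeks, which reactivity to the monitor could disturb. At follow-up, the finding is that the order is unspecified. An error there has not been shown.

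The effect is to weaken one of three self-report comparisons. The plan's sample size and its device-measured outcome are not touched.

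**What to change.** State when the IPAQ sitting item is completed and what period it covers. Complete it at the end of each 7-day wear, with the recall period worded as the monitored days.

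- **Baseline:** use the existing treadmill visit before the first class, one week after the monitor is issued, and complete the item before randomization.
- **Follow-up:** add the item to the last day of the FITS log, or collect it when the monitor is returned. The log is the safer route because the protocol describes no return visit.
- **CR intake item:** leave it where standard care has it, and describe its comparison with the activPAL3 as not same-week.
- **Analysis:** name the agreement analysis for each self-report measure; section 5.6.2 gives none.

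The cost is a few minutes, with no additional visit or device. There are two drawbacks. The 30-minute pre-class slot already holds a treadmill test of 10 to 15 minutes. A week of daily logging may also influence the IPAQ answer, which the report should acknowledge.

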5.4.2 Intervention

Following the baseline phase and the sub-maximal exercise test, participants will be randomized in a 1:1 ratio to: 1) usual care (C), 2) usual care + sedentary prompts from the VTAP monitor (I) using a computer-generated, stratified by sex, random sequence. Treatment assignments will be generated and placed in sealed, numbered envelopes to ensure concealment until baseline data is collected.

Both groups will complete a combination of supervised and home-based exercise sessions over an 8-week period (as per standard CR programming). Supervised exercise sessions will take place at the Minto Prevention and Rehabilitation Centre at the UOHI.

Intervention Group participants will also be provided with a VTAP monitor to wear directly on the skin of the front of their right thigh during waking hours for weeks 1 through 7. The monitor will provide participants with real-time feedback on their sedentary behaviour. The VTAP is the world's first commercially available device for free-living sedentary behaviour modification. The VTAP alerts wearers to the fact they have been sitting for a period of time and ought to move. The alerts are delivered by way of gentle vibrotactile feedback (buzzing). The monitors will be programmed to provide feedback once the wearer has been sedentary for 30 consecutive minutes. The monitors will also be able to log the duration and intensity of the primary movements including: sedentary, upright and ambulatory activities of the intervention participants. Due to the battery life of the monitors, each week participants will be provided with a newly charged VTAP and sticker applications at the first CR session of the week. See the product information sheet for the *activPAL3™* VTAP Specifications.

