5.6.2 Analysis strategies

Baseline clinical and socio-demographic characteristics will be compared between groups to identify any chance differences that may have occurred despite random assignment. Outcome variables will be screened to determine whether they meet assumptions of normally distributed random variables with equal variances, and a descriptive examination will be performed, including plotting of relationships by condition. Retention rate will be computed by condition.

For the primary analyses, group differences in objectively measured and self-reported sedentary time (using the average of seven days) over the two time points (baseline and 8 weeks) will be examined using independent t-tests for parametric variables and Wilcoxon Mann Whitney test for nonparametric

variables. Similar analysis techniques will be used for secondary outcomes of interest (i.e., *activPAL*-measured and self-reported weekly MVPA; BMI, waist circumference, total cholesterol, HDL, LDL, triglycerides, fasting blood glucose, blood pressure, resting heart rate, aortic stiffness, HRQoL scores, self-efficacy scores, HADS scores, and maximum aerobic capacity).

Table 1. Study measurement timeline.

Visit	Screen	Baseline week	Cardiac rehabilitation							
			Week 1	Week 2	Week 3	Week 4	Week 5	Week 6	Week 7	Week 8/ follow-up
Length of time needed	30 min	1-2 hours	45 min	30 min	30 min	30 min	30 min	30 min	30 min	1-2 hours
Informed consent	C, I									
Diagnosis	C, I									
Age	C, I									
Sex (male/female)	C, I									
Height		C, I								
Weight		C, I								C, I
Waist circumference		C, I								C, I
Blood pressure (Mobil-O-Graph)		C, I								C, I
Resting heart rate (Mobil-O-Graph)		C, I								C, I
Blood work (cholesterol, HDL, LDL, triglycerides, HbA1c)		C, I								C, I
MVPA (CR questionnaire + activPAL3)		C, I								C, I
Questionnaires (self-efficacy, HRQoL, anxiety/depression)		C, I								C, I
Aortic stiffness (Mobil-O-Graph)		C, I								C, I
Aerobic power (Bruce Treadmill Test)			C, I							C, I
Sedentary time (activPAL3™, IPAQ, CR Questionnaire)		C, I								C, I
7-day activity journal (FITS)		C, I								C, I
Wear-time log			I	I	I	I	I	I	I	
Sedentary feedback (VTAP)			I	I	I	I	I	I	I	
Feedback survey										C, I

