6.2 Risks, benefits and usual standard of care

No changes will occur to the usual standard of care for patients enrolled in CR.

Participation in this study requires that participants wear an *activPAL3™* monitor taped (using stickers) to the front of the right thigh during waking hours for a minimum of 7 consecutive days (baseline and follow-up) and the VTAP monitor continuously during waking hours for weeks 1-7 in the intervention group. The PALstickies used to apply the *activPAL* devices are hypoallergenic and consist of a dual layer hydrogel that does not pull at skin or hair. They are used for waking day recordings and are removed when going to bed, showering or bathing and will therefore, be reapplied each morning. In order to reduce possible skin irritations, participants in the intervention group will be instructed to alternate the location and leg used over weeks 1-7. The monitors are not an intentional emitter or radiator of electric or magnetic fields and poses no risk to a person fitted with a pacemaker. Important to note however that there are some limitations to when the monitor can be worn during scans and testing. The table below outlines when it should be removed and will be provided in the information sheet to participants:

Scan/test	Affects activPAL	activPAL affects scan	Comment/action
MRI scan	YES	YES	Remove from test
CT scan	YES	YES	Remove from test
X-ray	NO	Yes if in imaged area	Remove if in imaged area
EMG	NO	MAYBE if in test area	Remove if thigh is tested
ECG	NO	NO	ECG electrodes are on chest
EEG	NO	NO	EEG electrodes are on chest

Participation in this study requires that participants perform an exercise test (Modified Bruce Treatment Test) and training sessions. The risk of cardiovascular events during exercise testing varies directly with the incidence of cardiovascular disease. The risk of exercise testing is low, with approximately 6 cardiac events per 10,000 tests (0.06%). This is comparable to the usual care that patients in cardiovascular rehabilitation programs would receive. Recent studies have reported a rate of 1 cardiac arrest per 116,906 patient-hours, 1 myocardial infarction per 219,970 patient-hours, 1 fatality per 752,365 patient-hours, and 1 major complication per 81,670 patient-hours in a cardiovascular rehabilitation setting. It should be noted that these rates are low and

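### The week-8 activPAL3 and FITS comparison estimates what remains after prompts end but is worded as change over the intervention; adherence is planned from participant logs although the VTAP can log activity

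*Combined protocol and SAP*

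**What the plan says.** **When prompts are given.** Section 5.4.2 has intervention participants wear the VTAP "directly on the skin of the front of their right thigh during waking hours for weeks 1 through 7". Section 6.2 agrees: "the VTAP monitor continuously during waking hours for weeks 1-7 in the intervention group". In Table 1 the rows for VTAP feedback and for the wear-time log have entries in CR weeks 1 to 7 and none at week 8.

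**When the outcome is measured.** Section 5.1: "Follow-up sedentary time measures will be taken at the end of CR (during Week 8 of CR/Week 9 of the RCT". Both arms then wear the activPAL3 for seven days. Table 1 places the FITS journal at baseline and week 8 only. Section 5.6.2 compares the arms on these occasions alone, "over the two time points (baseline and 8 weeks) will be examined using independent t-tests".

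**How the outcome is worded.** Section 5.5 describes the primary outcome of the intervention as change in sedentary time "over the 8-week intervention period" and adds: "These outcomes will provide standard deviations to estimate an effect size for a future RCT". One paragraph of 5.1 gives the length of the intervention first as 8 weeks and then as 7.

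**Adherence.** It is one of four feasibility measures listed in 5.5 under the primary objective, and its stated source is the wear-time log. Participants complete the log and return it weekly (5.4.3, Intervention assessments). Section 5.4.2 says that the VTAP is able to log time sedentary, upright and walking. The device is exchanged each week, for reasons of battery life. No listed measure uses its record.

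**The concern.** A prompt that fires after 30 sedentary minutes could act in two ways. It could shorten sitting while it is switched on, or it could change habits that last after it is taken away. These are different effects, and activPAL3 and FITS are scheduled to observe only the second.

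The outcome wording in 5.5 does not tell the reader this. Someone who takes it at face value would read the week-8 difference as the effect of prompting during the intervention. If that difference is near zero, activPAL3 and FITS cannot separate prompts that do nothing from prompts that work only while worn. The trial exists to inform a larger one, so it matters which of the two effects is handed on.

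The second matter concerns a feasibility measure. How long participants wore the prompting device is central to judging feasibility, and the plan takes it from the participants' own account. The device itself is described as able to record activity and comes back to staff every week.

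**Working it through.** The plan states no figure on this point, so there is none to reproduce. The check lays the schedule out in whole weeks.

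| Study week | CR week | VTAP prompts (intervention arm) | activPAL3 and FITS (both arms) |
|---|---|---|---|
| 1 | baseline week | no | 7 days |
| 2 to 8 | 1 to 7 | yes | none |
| 9 | 8 | no | 7 days |

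Inputs: prompted weeks from 5.4.2, 6.2 and Table 1; measurement weeks from 5.1 and Table 1; total duration of 9 weeks from 5.4; 16 participants per arm from 5.6.1.

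- Study days: 9 × 7 = 63.
- Prompted days per intervention participant: 7 × 7 = 49.
- activPAL3 and FITS days: 7 + 7 = 14.
- Overlap between the 14 measured days and the 49 prompted days: 0.
- Scheduled VTAP wear at full retention: 16 × 7 = 112 device-weeks, or 16 × 49 = 784 participant-days. None of it feeds a listed measure.

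The zero overlap rests on whole-week boundaries. The documents do not state the day on which the last VTAP is handed in, so a small overlap at the turn from week 7 to week 8 cannot be ruled out.

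The wording can be set against this calendar:

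- Section 5.4.3 (Follow-up assessments) places the end of the intervention after 8 weeks of the study. One baseline week plus seven prompted weeks is eight, so this label fits and is not an error.
- Section 5.5 gives an intervention period of 8 weeks. VTAP wear is scheduled for seven, and the follow-up week lies outside them.
- Section 5.1 uses both 8 and 7 weeks in one paragraph. The 8 is tied there to the length of the CR programme, which may explain it, but the two are not reconciled.

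No power figure is offered. It would need the share of any effect that persists into week 8, and the documents give none.

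**The case against.** The case against giving this much weight is a fair one.

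- **The timing is open and may be intended.** The text and Table 1 agree on it, and both arms wear the same non-prompting monitor at follow-up. Section 5.1 asks whether 7 weeks of intervention is enough and cites reductions seen following interventions of 4 to 24 weeks. The Introduction says that prompts work by raising awareness of movement, which could outlast the vibration. This stands: the timing is not a fault, and there is no call to move the measurement.
- **This is a feasibility pilot of 32 people.** Section 5.6.1 says that such studies are generally not powered for intervention effects, so an ambiguous null does limited harm. This stands as a limit on the weight of the point. It does not remove the need to say which effect is being estimated.
- **Relabelling does not recover the missing estimate.** True. It only prevents a wrong reading.
- **A log is a defensible pilot choice.** The device comes off for bed and bathing (6.2), so a log is needed to interpret gaps in any record. The plan does not say that logs are the only source, and it does not describe storage or download of VTAP data. This stands to the extent that the device-based step must be conditional on retrieval and must keep the log. Even so, no use of the VTAP record is planned, and if available it is a more direct measure of wear than self-report alone.

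**Conclusion.** The point holds as one of labelling, with a conditional improvement to adherence. As scheduled, the activPAL3 and FITS between-arm contrast is a post-prompt effect: 0 of 49 prompted days are observed, assuming whole-week boundaries. The wording in 5.5 and the two intervention lengths in 5.1 do not match that. Adherence is planned from self-completed logs although up to 112 device-weeks of VTAP wear are scheduled.

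A reader might infer more than the documents support:

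- *That purpose 3 is unmet.* Section 2.0 wants "to describe changes in sedentary time that occur over standard CR with the use of prompting cues from the VTAP". Change from baseline to the end of CR in the prompted arm answers this; it does not require measurement while prompts are on.
- *That the standard deviations for the next trial are compromised.* Section 5.5 speaks of standard deviations, and nothing in the documents shows that week-8 timing distorts them.
- *That the other self-report items share the problem or lack a recall window.* Section 5.5.1 also lists "sitting time from the International Physical Activity Questionnaire" and a sitting question from the CR questionnaire. Those forms were not available for review, so their recall periods are unknown here and no gap in the plan can be asserted. The point is confined to activPAL3 and FITS.
- *That VTAP data could supply the missing effect.* The control arm has no VTAP record, and CR itself may change sedentary time, which is secondary objective 2 in 4.2.

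**What to change.** 1. **Label the estimate.** In 5.5 and 5.6.2, state that the week-8 activPAL3 and FITS contrast is an effect measured after prompts have ended, and that a null result is not to be read as prompts having no effect while in use. Reconcile the passages in 5.1, 5.4.2, 5.5 and 6.2 that give or imply 7 and 8 weeks of intervention. The cost is wording only.
2. **Use the device record if it can be had.** Check the VTAP specification that 5.4.2 refers to.
   - If the record can be retrieved at the existing weekly exchange, download it. Define adherence from device-recorded wear (days worn out of those scheduled, and hours per day), with a non-wear rule fixed in advance and supported by the log. Report VTAP sedentary time in weeks 1 to 7 as a within-arm description only, not as an effect of prompts.
   - If it cannot be retrieved, keep the log and report adherence as self-reported.

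Step 2 costs up to 112 device-week downloads, a written non-wear rule and some descriptive analysis. It needs no new visit, device or participant task. Neither step yields a randomised estimate of sedentary time under prompting, and the report should say so.
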